## **II. SUBJECT SELECTION**

In phase II, we will recruit about 80 subjects in order to randomize 40 patients with NSCLBP for this study. Subjects will need to meet all of the following inclusion criteria and none of the following exclusion criteria:

Inclusion Criteria:

1. Providing informed consent to participate in the study
2. 18 to 85 years old
3. Having non-specific chronic low back pain as defined by [6, 7] (existing pain for at least 3 months and having pain on at least half the days in the past 6 months) with an average of at least 3 on a 0-10 VAS scale
4. Pain resistant (partial or no response) to common analgesics and medications for chronic pain such as Tylenol, Aspirin, Ibuprofen, Soma, Parafon Forte DCS, Zanaflex, and Codeine
5. Must have the ability to feel sensation by Von-Frey fiber on the forearm

Exclusion Criteria:

1. Subject is pregnant
2. Contraindications to tDCS in conjunction with TUS:
  - a. Metallic implant in the brain
  - b. Implanted brain medical devices
3. History of alcohol or drug abuse within the past 6 months as self reported
4. Use of carbamazepine within the past 6 months as self reported
5. Suffering from severe depression (with a score of >30 in the Beck Depression Inventory)
6. History of neurological disorders as self reported (including epilepsy (note patients will also be evaluated via EEG at baseline and any patient showing abnormal EEG activity will be removed))
7. History of unexplained fainting spells as self reported
8. History of severe head injury resulting in more than a momentary loss of consciousness as self reported
9. History of neurosurgery as self reported
10. Unstable pain (defined as a difference in pain intensities larger than 4 points on a 0-10 VAS scale between the average over the week prior to visit 2 and the average over the week prior to visit 4a [96])
11. Large placebo responder: having a reduction of pain greater than 72.52% (VAS pain now post stimulation on V3 compared with VAS pain now pre stimulation on V2) or VAS now of 0 or 1 following any stimulation during Run-in period.
12. Low Adherence during the Run-in stimulation visits (ie. not attending both Run-in stimulation visits within approximately one week)
13. Low baseline pain: VAS pain weighted average < 3 prior to randomization during visit 4a

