### **III. STUDY PROCEDURES**

Because our protocol involves a run-in phase (Part I), we expect that up to 90 patients may enter the run-in phase so we will be able to randomize 40 eligible subjects to participate in this study (in phase II). When the target number of 40 subjects (for phase II) entering the randomized phase

(Part II) is completed, enrollment will end. Subjects who passed the run-in phase (Part I) successfully will then be randomly assigned to receive treatment in Part II with active tDCS+active TUS (n=20) or sham tDCS+sham TUS (n=20 inactive transducers).

**General Study Outline:** This two-Part study will consist of 23 visits over the course of about 15 weeks. After Visit 1, the remaining Part I of the study will take about a week (Visits 2-4a). Prior to any assessments, the subject will consent to participate in both Part I and Part II, pending that the subject fits the additional eligibility criteria\* of the run-in period. After completion of Part I, eligible subjects will continue onto Part II, the main interventional portion of the trial. Part II of the study will take place over the remaining weeks (Visits 4b-23).

*Part I Study Flow – Run-in Period (Visits 1-4a):*

- Screening Visit
- Run-in Visit 2&3 – sham stimulation visits
- Rescreening Visit

*Part II Study Flow – (Visits 4b-23):*

- 10 sessions of tDCS stimulation over 2 weeks
- Bi-weekly sessions of tDCS stimulation over 3 weeks
- 4 Follow-Up Visits – 2 week, 4 weeks, 6 weeks, and 8 weeks post-stimulation

Eligibility criteria for Part II include:

- VAS pain score greater than 1 following either of the two SHAM stimulation sessions [97] during Part I and pain reduction not greater than 72.52% (i.e. not a large placebo response)
- Stable pain intensities (defined as a difference in pain intensities less than or equal to 4 (on a 0-10 VAS scale) between the average over the week prior to visit 2 and the average over the week prior to visit 4a [96])
- High adherence during the Run-in stimulation visits (defined as completing both Run-in stimulation visits within approximately one week)
- VAS pain weighted average  $\geq 3$  prior to randomization during visit 4a (i.e. not exhibiting low baseline pain)

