### **Visit 4a**

Rescreening Visit – (Approx Time: 1 ¼ hours)

*This study will be scheduled ~1 week after the first baseline measurements were done.*

The subject will complete a series of assessments:

- Urine pregnancy exam (if applicable)
- Visual Analog Mood Scale (VAMS)
- Mini Mental State Examination (MMSE)
- Stroop test
- Neurological and Physical Exam
- Visual Analogue Scale (VAS) for Pain
- Pain/Medication Diary
- Quantitative Sensory Testing (QST)
- Walking Test
- Postural Stability/Standing Test
- One Leg Stance Test
- Trunk Mobility Test
- Screening form for part II\*

\* If the subject is eligible for part II, then they will complete visit 4b in the same day.

Note, patients who exhibit large placebo effects (defined as exhibiting VAS=0 or VAS=1) following either of the two SHAM stimulation sessions[97] during Part I and score reduction higher than 72.52%; unstable pain intensities (defined as a difference in pain intensities larger than 4 (on a 0-10 VAS scale) between the average over the week prior to visit 2 and the average over the week prior to visit 4 [96]), low baseline pain (defined as weighted VAS avg < 3) prior to randomization during visit 4) or who are not compliant with the Run-In protocol (defined as not completing both Run-in stimulation visits within approximately one week) will be excluded from the full trial [96-98], and thus will not receive MRIs and will not come for

additional visits. By following this Run-in strategy, we will maximize trial resources by excluding patients who demonstrate poor compliance and are less likely to complete the trial. More importantly, we will increase the likelihood that the effects we are measuring in the full trial are biological in nature and directly caused by the stimulation intervention [97, 98]. Note, a patient can be screened out in any of the visits prior to Visit 4b.

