#### **IV. BIOSTATISTICAL ANALYSIS**

Data forms and questionnaires will be coded in a standardized manner, and double-entered into our database. Digital measures/recordings will be similarly tracked in our database and regularly backed up. Analyses will be conducted using standard statistical software such as SAS and Matlab.

Sample size calculations and data analysis:

*Aim 1:*

For planning sample size calculation for this study, we considered the surrogate pain outcomes as the main outcome for such analysis; considering the two studies showing significant alterations of these outcomes in NSCLBP [118], an effect in the active tDCS in conjunction with active TUS that is twice of the effect in SHAM tDCS in conjunction with SHAM TUS would be adequate. Considering this effect size and a power of 80% and alpha of 5%, we would need 6 subjects per group for a total of 12 subjects. Therefore considering dropouts and also to increase the sample in phase I for the clinical outcome, we increased the sample to 20 subjects (10 for each arm), that would also give a power to detect significant differences of 2 points in VAS between the 2 groups; though the clinical outcome is not the main outcome in phase 1. For Phase 2, we doubled the sample size as to have enough power to detect a difference of 1.3 in VAS between the two groups that would therefore be adequate to demonstrate a clinically meaningful difference between the two groups. We considered differences smaller than that not clinically meaningful.

All analyses will be conducted according to the principle of intention-to-treat (using regression-based single imputation method). We will also perform an additional sensitivity analysis in

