which we will use the method of last observation carried forward. The primary outcome will be TS and CPM [118] (in phase 1) and VAS (in phase 2) changes as indexed by VAS scores, biomechanical function changes as indexed with the motion analysis suite, and global self-assessment changes. Differences between the two groups (active tDCS in conjunction with active TUS and SHAM tDCS in conjunction with SHAM TUS) will be tested using Student's t-test and, in addition, we will adjust for important baseline variables and also test the time effect in general mixed longitudinal models. This model will be used for the primary and secondary outcomes. Secondary analyses will be conducted in an exploratory manner (no correction for multiple comparisons). Similar analysis will be conducted for the adverse effects measuring continuous outcome and for the categorical outcomes we will use Fisher's exact test. In both cases, for safety analysis we will use uncorrected p-value to increase the likelihood of detecting detrimental adverse effects.

332-6.

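### The Phase II primary VAS hypothesis is tested two ways with no rule for which decides, and no visit, reading or VAS version is named.

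*Combined protocol and SAP*

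**What the plan says.** Section IV (Biostatistical Analysis, Aim 1) states the Phase II primary outcome as "VAS (in phase 2) changes as indexed by VAS scores, biomechanical function changes as indexed with the motion analysis suite, and global self-assessment changes". The groups are then compared by a Student's "t-test and, in addition, we will adjust for important baseline variables and also test the time effect in general mixed longitudinal models". The next sentence adds: "This model will be used for the primary and secondary outcomes". The sample-size paragraph says: "For Phase 2, we doubled the sample size as to have enough power to detect a difference of 1.3 in VAS". It attaches no visit, reading, VAS version or SD to that difference.

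The visit descriptions schedule VAS as follows:
- Visit 4b: once, after stimulation.
- Visits 5 to 19: before and after stimulation.
- Visits 20 to 23: once each.

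Two versions of the scale appear, both in eligibility rules. The placebo-response rule uses current pain at Visits 2 and 3. The low-pain rule uses a weighted average: "Low baseline pain: VAS pain weighted average < 3 prior to randomization during visit 4a". Section III and the Visit 4a text repeat that rule ("prior to randomization during visit 4a (i.e. not exhibiting low baseline pain"; "low baseline pain (defined as weighted VAS avg < 3"). Visit 4a is also timed about a week "after the first baseline measurements were done", which makes Visit 2 an earlier baseline.

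Under Randomization, allocation is stratified by run-in placebo effect above or below -17.3%. The analysis text does not mention that factor.

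**The concern.** The plan runs two tests of one primary hypothesis. With 20 per arm they can fall on opposite sides of 5%, and the plan has no sentence that settles which is the trial's answer. That problem arises even if nobody selects results.

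The second gap is that neither test can be run from the text as it stands. A statistician with the final dataset would have to choose the visit, the pre- or post-stimulation reading and the VAS version. If those choices are made after the data are seen, the nominal 5% level is no longer assured. Section IV states that level only in the calculation for the surrogate pain outcomes.

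**Working it through.** **Count of readings (visit descriptions).** Visit 4b: 1. Visits 5 to 19: 15 × 2 = 30. Visits 20 to 23: 4. Total 1 + 30 + 4 = 35 readings, over 1 + 15 + 4 = 20 visits.

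**The plan's own figure.** The plan says 20 per arm can detect 1.3 VAS points. With no SD given, this cannot be reproduced, so the SD is back-solved. Inputs: n = 20 per arm (Section III), difference 1.3 (Section IV), and the 5% alpha and 80% power that Section IV gives for the surrogate outcomes. A two-sided test is assumed.
- Normal formula: SD = 1.3 / [√(2/20) × (1.960 + 0.842)] = 1.3 / (0.3162 × 2.802) = 1.47.
- Noncentral t, 38 df: 80% power is reached at SD = 1.43, with noncentrality 1.3 / (1.43 × 0.3162) = 2.87.

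The t value, 1.43, is used below as the SD of the change score.

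**How the two tests relate at one visit.** Let the variances at baseline and follow-up be equal (σ²), with correlation r, which is assumed.
- SD of change = σ√[2(1 − r)].
- Residual SD after baseline adjustment = σ√(1 − r²).
- Ratio of residual SD to SD of change = √[(1 + r)/2].

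| r (assumed) | Ratio | Residual SD = 1.43 × ratio |
|---|---|---|
| 0.5 | 0.866 | 1.24 |
| 0.7 | 0.922 | 1.32 |
| 0.9 | 0.975 | 1.39 |

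The adjusted test is always at least as precise in this setting. The tests are highly correlated but not identical.

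**Simulation.** 20 per arm, complete data, two-sided 5%. Baseline-adjusted ANCOVA at one visit stands in for the mixed-model contrast at that visit. The stratification factor is not simulated.

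| r (assumed) | t-test power at 1.3 | Adjusted power at 1.3 | Only adjusted significant | Only t-test significant | Tests disagree | Type I error if either accepted |
|---|---|---|---|---|---|---|
| 0.5 | 80% | 89% | 10.7% | 1.7% | about 12% | about 7.4% |
| 0.7 | 80% | 85% | 7.1% | 2.1% | about 9% | about 6.8% |
| 0.9 | 80% | 81% | 3.2% | 2.3% | about 5.5% | about 6.1% |

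Each test alone holds close to 5% under no effect. Repeat runs move the last column by about 0.2 points or less.

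**Text check on the rest.** No sentence in the visit descriptions, the assessment descriptions or Section IV selects a visit, a reading or a VAS version for the group comparison. The versions are distinguished only in the eligibility rules.

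**The case against.** Much of the plan's intent can be inferred. The t-test is named first and the model is introduced as an addition, so a reader may take the t-test as primary. Supportive analyses that sometimes disagree with the main one are normal. That inference is reasonable, but the plan does not state it, and the following sentence applies the model to the primary outcome as well. Even if it is granted, the visit, reading and VAS version remain open.

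Stronger readings are tempting and should not be pressed:
- **Three co-primary outcomes.** The sentence lists biomechanical function and global self-assessment beside VAS. But it speaks of one primary outcome, and Phase II is sized on VAS.
- **No baseline.** Eligibility text calls the Visit 4a value baseline pain, Visit 4b follows on the same day, and randomisation comes after all baseline evaluations. Visit 4a is strongly implied for VAS.
- **No treatment contrast in the model.** The sentence is about differences between the groups, with time tested as well. A group contrast is the natural reading; what is missing is the visit to which it applies.
- **Large multiplicity from 35 readings.** That would require picking results afterwards, which the documents do not describe. They also call secondary analyses exploratory.

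The source is also incomplete. The opening part of the document and the research strategy cited under Pain-Pressure Tests are not available and could answer some of this.

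**Conclusion.** The point holds in limited form. In the text available, the Phase II primary comparison has two analyses without a deciding rule, and no visit, pre- or post-stimulation reading or VAS version is fixed.

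Under the stated assumptions, conflicting answers would occur in roughly 5.5% to 12% of trials when the true effect is 1.3 points. Type I error would be about 6.1% to 7.4% only if either result were accepted. These figures rest on the back-solved SD of 1.43, equal variances, complete data, one visit and assumed correlations of 0.5 to 0.9. Choice of visit or reading would add to the error only if results were picked after the fact.

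The point does not extend to missing data, where single imputation is the main method and last observation carried forward is the sensitivity analysis. The absent SD behind the 1.3-point figure is a separate matter. Confidence is moderate because the source is incomplete.

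**What to change.** Before unblinding, state in Section IV that:
- VAS is the sole Phase II primary outcome, defined as change from the Visit 4a value in one named VAS version to one visit and reading. The sponsor chooses these. The same version must be recorded at both visits.
- The deciding analysis, at two-sided 5%, is the treatment contrast at that visit from the mixed model, adjusted for Visit 4a VAS and for the randomisation stratum (placebo effect above or below -17.3%).
- The t-test is supportive.
- VAS at other visits, biomechanical function and global self-assessment are secondary.

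The adjusted contrast is preferred because it was at least as powerful as the t-test at every correlation examined and uses data already collected.

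The change is to wording and adds no visits or assessments. It does not establish that 40 subjects are enough, since that depends on the unstated SD. The cost to the sponsor is that significance on the t-test alone, or at another visit, no longer counts as primary success.

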#### *Randomization:*

Once eligibility and consent have been approved and completed, after all baseline evaluations and immediately before the first stimulation session of Part II, stratified blocked randomization will occur using the randomized list generated by an automatic web-based randomization program ([www.randomization.com](http://www.randomization.com)). Randomization will be based on placebo effect above or below -17.3% according to preliminary data. A staff member who is not involved in any of the study procedures will be responsible for creating the randomization list and monitoring it during the study. Subjects will be randomly assigned to treatment or placebo groups in a 1:1 allocation ratio. We will use permuted blocks of variable sizes (4) in a random manner to minimize the risk of study staff guessing at the next allocation. Randomization order will be kept in sealed envelopes.

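### The primary VAS comparison has two analyses, a t-test and an adjusted mixed model, with neither made decisive and neither the randomisation stratum nor baseline VAS named as a covariate

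*Combined protocol and SAP*

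**What the plan says.** Under Randomization, "stratified blocked randomization will occur using the randomized list", and the stratification factor is the run-in response to sham: "Randomization will be based on placebo effect above or below -17.3% according to preliminary data". Exclusion criterion 13 in Subject Selection shows that VAS is also measured and used just before allocation: "Low baseline pain: VAS pain weighted average < 3 prior to randomization during visit 4a".

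The Biostatistical Analysis section defines the phase 2 primary outcome as "VAS (in phase 2) changes as indexed by VAS scores", without a visit. It tests the arms with Student's "t-test and, in addition, we will adjust for important baseline variables and also test the time effect in general mixed longitudinal models". The next sentence reads "This model will be used for the primary and secondary outcomes". The covariates are described only in the phrase "we will adjust for important baseline variables". The sample size text says that for phase 2 "we doubled the sample size as to have enough power to detect a difference of 1.3 in VAS between the two groups"; it gives no SD.

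**The concern.** Two analyses are assigned to one primary outcome, and no sentence ranks them. If the t-test gives p = 0.07 and the adjusted model p = 0.04, or the reverse, the plan does not say whether the trial is positive. The open covariate list adds to this freedom, because the adjusted model can be settled after the data are seen.

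There is also an efficiency question. The sponsor stratified on placebo response, presumably because it is expected to predict outcome, and will hold a pre-randomisation VAS for everyone. An unadjusted t-test uses neither as a covariate. Because the outcome is a change, the t-test already subtracts baseline, so the issue is not failure to account for baseline. Subtracting baseline is less efficient than adjusting for it. With 20 patients per arm, the difference in power can be material.

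**Working it through.** **Inputs from the documents.** 20 per arm; 1:1 allocation; stratified blocks of 4; phase 2 difference 1.3 VAS points; phase 1 difference 2 points with 10 per arm; alpha 5% and power 80% (stated for the surrogate outcomes, taken here to apply to VAS; two-sided assumed).

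**The plan's own figure.** It cannot be reproduced directly because no SD is given. Solving the noncentral t for 80% power gives an SD of 1.43 for 1.3 points with 20 per arm, and 1.51 for 2 points with 10 per arm. An SD near 1.5 is therefore a fair working value. Whether it describes raw scores or changes is unknown, so both are shown.

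**Change score against adjustment.** With equal raw SD σ at both times and correlation r, the change has variance 2σ²(1-r) and the baseline-adjusted outcome has variance σ²(1-r²). The ratio is (1-r²)/(2(1-r)) = (1+r)/2, which is 0.65, 0.75 and 0.85 at r = 0.3, 0.5 and 0.7. At r = 0.5 and σ = 1.5:
- change SD = 1.5 × √(2 × 0.5) = 1.5; SE = 1.5 × √(2/20) = 0.474; 1.3/0.474 = 2.74; power 76%.
- adjusted SD = 1.5 × √0.75 = 1.30; SE = 1.30 × √(2/20) = 0.411; 1.3/0.411 = 3.16; power about 86% after allowing for the two covariates.

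**Effect of the stratum.** Stratified blocking balances the stratum between arms, but the t-test leaves its variance in the error term. If it explains 20% of outcome variance at r = 0.5, the change variance of 2.25 contains 0.45 that does not contribute to the true error of the arm difference. The true SE is then about √(1.80 × 0.1) = 0.424, against a reported SE of about 0.474. In simulation (unequal stratum sizes, incomplete blocks) these are 0.428 and 0.473, so the reported SE is about 11% too wide. At 9% they are 0.450 and 0.472. At 0% there is no bias (0.476 and 0.471).

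**Power by simulation.** 40 patients, two strata with membership probability 0.5, t-test on change against ANCOVA on baseline and stratum, true difference 1.3, 5,000-6,000 trials per scenario. Cells give power (%) when the stratum explains 0 / 9 / 20% of outcome variance.

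| Assumed SD | r | t-test on change | ANCOVA |
|---|---|---|---|
| (A) raw score 1.5 | 0.3 | 62 / 63 / 62 | 78 / 84 / 87 |
| (A) | 0.5 | 76 / 77 / 79 | 86 / 89 / 95 |
| (A) | 0.7 | 93 / 95 / 96 | 96 / 98 / >99 |
| (B) change score 1.43 | 0.3 | 80 / 80 / 82 | 93 / 95 / 98 |
| (B) | 0.5 | 80 / 81 / 82 | 89 / 92 / 96 |
| (B) | 0.7 | 80 / 82 / 85 | 84 / 92 / 97 |

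A 30/70 stratum split at r = 0.5 under (A) gives the same picture: 76 / 77 / 79 against 86 / 90 / 94.

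**Type I error by simulation** (10,000 trials per scenario). For the t-test alone at r = 0.5 it is 5.2 / 3.7 / 3.1%, so it is valid, and conservative when the stratum is prognostic. A single pre-named ANCOVA stays near 5%. Reporting whichever p-value is smaller gives 5.6-8.0%. Under the null both tests are unaffected by scale, so this range covers nine distinct combinations of r and stratum strength. In a parallel run with a stratum effect of 0 or 1 point, the two tests disagreed on significance in 3-6% of null trials and in 5-25% of trials with a true 1.3-point effect.

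**The case against.** The best counter-reading is that the words joining the two analyses make the t-test the lead and the model supplementary, and that the sentence applying the model to the primary outcome gives its scope, not its rank. On that reading there is no choice between p-values and the inflation disappears. The reading is reasonable, but the text does not state it. It would also leave the less efficient test in charge and ignore the stratified design.

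Several limits stand:
- The t-test creates no false-positive risk. The 5.6-8.0% arises only if the result is selected, and the inflation is largest when r is low and the stratum is not prognostic.
- SD, correlation and stratum strength are all assumed. Under (B) the t-test keeps its planned power, so the loss is only relative to the adjusted model.
- A single-visit ANCOVA stands in for the mixed model; the planned longitudinal model itself was not simulated.
- The stratum derives from VAS change during the run-in and may be related to Visit 4a VAS, so their gains may overlap. This was not varied.
- Both variables could fall within the plan's general phrase about baseline adjustment. The point is that they are not named, so nothing obliges their inclusion.

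**Conclusion.** The concern holds. The plan applies an unadjusted t-test and an adjusted mixed model to the same primary outcome without saying which decides. It also fixes neither the -17.3% stratum nor Visit 4a VAS as a covariate. This is a specification and efficiency fault; it does not make either test invalid. With a raw SD of 1.5 and correlations of 0.3 to 0.7, leading with the t-test costs from about 3 points of power to 25 (96 against 93% at r = 0.7, 87 against 62% at r = 0.3). If 1.43 is the SD of change, the t-test has 80-85% and adjustment would give 84-98%. Selecting the smaller p-value would raise type I error to 5.6-8.0% for this one covariate set. The unnamed covariates and visit leave further choices that this figure does not include. It should be corrected before unblinding; confidence in the sizes is medium because the inputs are assumed.

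**What to change.** State one primary analysis: the arm difference in VAS at a single named visit, from the planned mixed model (arm-by-visit contrast) or from ANCOVA, adjusted for Visit 4a VAS and the -17.3% placebo-response stratum. The sponsor must choose the visit, because the documents give none. It must also say which Visit 4a measure is the covariate, since the eligibility criteria use both a weighted-average VAS and a current-pain VAS; the version matching the outcome is the natural choice. List any other covariates, and label the t-test as a supportive unadjusted result.

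The cost is SAP wording and those two decisions. Both covariates are known before randomisation, and neither visits nor sample size changes. If neither covariate is prognostic, the planned noncentrality of 1.3/(1.43 × √0.1) = 2.875 falls to 2.875 × √(36/37) = 2.836 through chance baseline imbalance, and the degrees of freedom drop from 38 to 36. Power then goes from 80.0% to 78.8% (79.7% to 78.6% in simulation).
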